### VR Hardware Placement and Cleaning

The Samsung gear device will be put in place as follows:

1. Patient places sanitary hair cap on head
2. Goggle is fitted with disposable sanitary cover and foam backing that affixes with Velcro to inside of face mask
3. Patient places goggle headset on him/herself and adjusts straps.

Between patients, the device will be cleaned as follows:

1. Headset will be removed; and disposable head cap, sanitary cover and foam backing will be thrown in sanitary waste bin in inpatient room.
2. Fabric strap will be cleaned by coordinator using Virex, approved cleaner for medical fabrics and let sit for a minimum of 10 minutes before next use.
3. Plastic housing of device will be cleaned using Sani-wipes and let sit for a minimum of 2 minutes before next use.
4. Inside and outside of the lenses of device will be cleaned using approved lens cleaner containing alcohol.

### VR Software

Next, we will continue to work with AppliedVR to develop appropriate VR environments for use by laboring patients. We will refine these environments given feedback from CSMC staff. These environments are not being developed specifically for any particular patient, and any participant may select any module. These modules will use 3D visual and audio cues to immerse the patient. Software modules may be used for as long as a patient wishes, but for this study, we are recommending 2-5 minutes for first use, and a maximum of 20 minutes for total use time per session.

Proposed VR interventions include the following:

1. Paint Studio: The patient will move his or her head around to paint an abstract image on canvas. Paint strokes are controlled by movement speed. Patients can also tour their own art studio.
2. TheBluVR: Patients select from several ocean environments (e.g., Arctic) by touching a trackpad on the side of the Gear VR goggles. Sea creatures swim up to the patient.
3. Concert Performance: Watch Cirque du Soleil perform from the stage. The patient can look around the environment in 360 degrees as the performance happens.
4. World Flyover: Patients fly over photorealistic views of world landmarks, allowing them to visit famous places from the hospital bed.

5. Pain RelieVR: Patients shoot at targets in an energetic cartoon world, while soothing music plays.

### **Outcomes and Data Collection**

Primary Outcome: Reduction in pain scores from pre- to post-intervention

Secondary Outcome:

1. Duration of use of the intervention
2. Acceptability of the intervention
3. Need for IV pain medication during the intervention
  - a. Time to IV pain medication after the intervention
4. Request for an epidural during the intervention
  - a. Time to epidural use after the intervention
5. Vital sign changes during and after the intervention including heart rate and blood pressure.

Data Collection

1. Baseline maternal demographics
  - a. Name and Medical Record Number (secured and stored separate from all other data below)
  - b. Age
  - c. Race/Ethnicity
  - d. Insurance status
  - e. Gravidity/Parity
2. Admitting diagnosis
3. Obstetric data
  - a. Gestational age
  - b. Induction agents
  - c. Mode of delivery
4. Vital Signs (blood pressure, heart rate) before, during (continuous pulse oximeter and blood pressure measurements every 10 minutes) and after the intervention.
5. Pain scores before and after the intervention. Average Pain Rating during 4 hours before intervention, and Average Pain Rating after intervention (up to 24 hours).
6. Pain interventions including time to first use of IV pain medication and first use of epidural.
7. Responses to **Quantitative Patient Survey** (PROMIS Global Health pre-intervention, and modified Childbirth Self-Efficacy Inventory pre- and post-intervention)

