We aim to perform a similar study to the latter above, but focused on relieving contraction pain in labor and delivery. We hypothesize that the use of virtual reality will reduce the patient's pain to a greater degree than no intervention. We will also qualitatively examine the subjects' satisfaction with and experience of virtual reality in labor and delivery as well as whether it had any effect on their need for pain medications or choice to receive an epidural.

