### Study Population and Period

The study population will consist of 40 patients: 20 in the VR arm and 20 in the Control arm (see below for sample size calculations).

We anticipate the recruitment and intervention portion of the study to be completed within 12 months.

The Inclusion criteria are as follows:

1. Female
2. >18 years old
3. English-speaking
4. Able to understand the goals of the study and provide informed consent
5. Pregnant with term gestation
6. Nullipara
7. Pain due to contractions rated from 4-7
8. Contractions at least every 5 minutes x 30 minutes preceding

The Exclusion criteria are as follows:

1. Parous
2. Use of medications for pain relief prior to the intervention
3. Use of an epidural
4. Preterm gestation
5. Pain not due to contractions
6. Pain score of 3 or below or 8 or above
7. Preeclampsia with severe features, eclampsia
8. History of epilepsy, dementia, or other neurologic disease that would prevent using VR
9. Sensitivity to flashing light / motion
10. Medical condition predisposing to nausea or dizziness
11. Injury to the eyes, face, neck, or arms that prevents comfortable use of VR hardware or software, or safe use of the hardware (e.g., open sores, wounds, or skin rash on face)

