## 8. Responses to **Qualitative Interview**

### Sample Size Calculations

We will compile data from qualitative interviews, and summarize key points about the intervention brought up by patients. This report will further guide development and refinement of the inpatient VR intervention.

We will also examine changes in scores on patient-reported pain, blood pressure and pulse rate. We will compute change scores for each of these measures and also compare these patients to the Control group. If data are normally distributed, we will use a paired Student's t test for comparisons pre- and post-intervention, and two-sample t tests for between group comparisons. If data are abnormally skewed, we will conduct similar analyses using the non-parametric Wilcoxon signed-rank test, and the Wilcoxon rank-sum test, respectively.

We are uncertain of the degree of change we will observe in patient responses to the Quantitative Patient Survey (PROMIS + CSEI), pain ratings, and cardiac vitals after exposure to the VR intervention, as a study of this type has not been previously conducted.

We have decided instead to use established, clinically-meaningful changes in pain ratings as a means of estimating change. Previous studies have shown that for the minimum clinically important difference in pain scores varies by baseline starting pain level. For those subjects starting with a baseline pain level of 40-70 mm (as in our planned cohort), the minimum clinically important difference is 13 mm (Olsen, BMC Medicine 2017).

For all analyses, we will assume a 5% Type I error rate (alpha) and a 20% type II error rate (or 80% power). If we assume that the baseline median pain level of our patients is 55 mm, then for within group analyses to show a 13 mm reduction in pain would require 20 patients in each arm for 40 patients total.

Therefore, to conduct one RCT of the effect of VR on pain starting at a median level of 55 mm, we would need 40 patients:

[Control (20 patients)]

[VR (20 patients)]

We will also perform between group analyses, we will compare pain scores obtained from all inpatients exposed to the VR intervention to the Control. Our calculated sample size will also be adequate to identify a difference between groups.

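### The hypothesis compares VR with control, but no between-arm contrast is primary, and 20 per arm is derived only for a within-group change

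*Combined protocol and SAP*

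**What the plan says.** The Background section gives the pain hypothesis as comparative: VR "will reduce the patient's pain to a greater degree than no intervention". Study Procedures describes a randomised controlled trial, and Study Population and Period sets 20 women per arm.

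Outcomes and Data Collection then gives "Primary Outcome: Reduction in pain scores from pre- to post-intervention". It does not say whether this is a change within the VR arm or a difference between arms.

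The Sample Size Calculations section holds both the analysis plan and the sample size. It plans paired tests before and after the intervention "and two-sample t tests for between group comparisons", with Wilcoxon versions for skewed data, and calls neither primary. The size is worked out "for within group analyses to show a 13 mm reduction in pain would require 20 patients in each arm", at 5% alpha and 80% power. On the comparison with Control it says "we will compare pain scores obtained from all inpatients exposed to the VR intervention to the Control", and then: "Our calculated sample size will also be adequate to identify a difference between groups". No SD, between-arm target difference or between-arm power is given. No adjustment for baseline pain is planned, although each woman gives a 0 to 10 pain score before the intervention.

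**The concern.** Because neither test is designated, the trial could report a significant fall within the VR arm as its primary result and stay within the protocol. That test does not answer the hypothesis. Women enter within a limited pain window ("Pain due to contractions rated from 4-7"), nobody is blinded, and a staff member stays with the VR user throughout. Progress of labour, the timing of contractions and staff attention can all move a pain score without any effect of VR. The control arm exists to remove these influences, yet the only test the trial was sized for does not use it.

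The sample size raises a second problem. For the same SD of change and the same difference, a two-sample comparison needs about twice as many patients per arm as a paired test needs in total. A number that is just enough for the paired test is therefore not enough for the between-arm test at the same 13 mm.

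A smaller point is the reference to women exposed to VR. It may be loose wording for the VR arm, but women may stop VR at any time, so the analysis set should be defined by randomisation.

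**Working it through.** **Inputs from the Sample Size Calculations section.** Difference 13 mm (1.3 points, reading the 0 to 10 scale as 100 mm), alpha 5%, power 80%, n = 20 per arm. The documents do not state sidedness (two-sided assumed) or the SD of change (back-solved below). Results use the noncentral t distribution unless noted.

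**1. The plan's own figure.** Without an SD, 20 per arm cannot be reproduced forward, so I solved for the SD that yields it.
- Normal approximation: SD = 13 × √20 / (1.960 + 0.842) = 20.75 mm.
- Paired t: noncentrality = (13/SD) × √20 on 19 df. Power is 80% at SD = 19.68 mm. Twenty is the smallest sufficient n for SDs from about 19.13 to 19.68 mm.

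**2. Between-arm test at that SD.** Noncentrality = (13/19.68) × √(20/2) = 2.09 on 38 df.
- Power for 13 mm at 20 per arm: 53%.
- Difference detectable with 80% power at 20 per arm: 17.9 mm.
- Patients per arm for 80% power at 13 mm: 37.

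One-sided, signed-rank and normal-approximation variants give 49% to 59% power and 35 to 41 per arm, so the choice of formula does not change the picture.

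**3. The other direction.** For 20 per arm to give 80% between arms at 13 mm, the SD must be at most 14.30 mm. At 14.30 mm the paired test has 77.5% power with 11 patients and 81.7% with 12, so it needs 12 rather than 20.

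**4. Range over assumed SDs, for 13 mm.**

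| SD of change (mm) | Paired n for 80% | Two-sample n per arm for 80% | Between-arm power at 20 per arm |
|---|---|---|---|
| 12 | 9 | 15 | 92% |
| 14 | 12 | 20 | 82% |
| 16 | 14 | 25 | 71% |
| 18 | 18 | 32 | 60% |
| 20 | 21 | 39 | 52% |
| 25 | 32 | 60 | 36% |

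**5. What the paired test can show with no VR effect.** For illustration, suppose both arms fall by the same amount. With SD 19.68 mm and n = 20, the paired test in the VR arm shows a significant reduction in 19%, 49% or 80% of trials for a common fall of 5, 9 or 13 mm.

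**6. Gain from baseline adjustment.** Residual variance = 19.68² − (1 − slope)² × (baseline SD)², on 37 df. I assumed a baseline SD of 8.7 mm (uniform over 40 to 70) or 11.2 mm (equal shares at 40, 50, 60 and 70), and slopes of 0.3, 0.5 and 0.7.
- Baseline SD 8.7 mm: power 57%, 55%, 54%; 34, 36, 37 per arm for 80%.
- Baseline SD 11.2 mm: power 60%, 56%, 54%; 32, 35, 36 per arm for 80%.
- Multiplying the variance by 1 + 1/36 for chance baseline imbalance lowers the power range to about 53% to 59%.

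The gain is modest because the entry window limits the spread of baseline scores.

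**The case against.** A between-arm analysis is clearly intended. The study is a randomised trial, change scores are to be compared with Control, and 5% alpha and 80% power are stated for all analyses. The adequacy sentence names no target, and 13 mm belongs to the within-group fall. It equals the between-arm difference only if control pain does not change. If control pain rose by 5 mm while VR pain fell by 13 mm, the difference would be 18 mm and power at 20 per arm about 80% at the same SD; a 3 mm rise gives about 71%. The SD is back-solved, and at 12 or 14 mm the power is 92% or 82%. Nothing in the documents says untreated pain falls over 30 minutes. A two-sample test of change scores is valid, so ANCOVA is a preference.

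Much of this stands as a limit on the claim. The 53% is conditional on 20 being the true paired requirement. The common-fall figures show a principle and do not predict this trial. ANCOVA is a refinement, and the wording about exposed women is minor. None of it supplies what is missing. The plan states no SD, no expected change in controls and no between-arm target, and 13 mm is the only difference it offers. Intending a between-arm test also does not make it the primary one.

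**Conclusion.** The concern holds. The hypothesis is between arms, the primary outcome names no contrast, and the sample size rests on a within-group test that cannot answer the hypothesis. The statement that 20 per arm also suffices between groups does not follow. At 13 mm, no single SD of change makes 20 the paired requirement and also gives 80% power between arms. The shortfall, 53% power against 80%, assumes a two-sided test, equal SDs in the arms, no dropout and an SD of about 19.7 mm. The size could still be adequate if the SD is about 14 mm or less, or if the expected between-arm difference is about 18 mm or more, but the plan claims neither. This should be corrected because it decides which test answers the trial's question.

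**What to change.** - In Outcomes and Data Collection, name a single primary analysis: the between-arm difference in post-intervention pain, two-sided 5%, by ANCOVA adjusted for the baseline 0 to 10 score, in all randomised women by assigned arm. Naming the already planned two-sample test of change scores as primary would also cure the core defect, at slightly lower power under the assumptions above.
- In Sample Size Calculations, define the VR comparison group as all women randomised to VR, and report within-arm changes descriptively.
- Replace the between-group adequacy sentence with the between-arm power or detectable difference at 20 per arm, stating the target difference and the sponsor's own SD with its source. If that SD were 19.7 mm, power for 13 mm would be roughly 53% to 60%, depending on the analysis.

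The cost is wording, using data already collected, with no extra patients or procedures at 40. The drawback is that the stated power will probably look worse. Restoring 80% for 13 mm at an SD of 19.7 mm would take about 32 to 37 per arm, which is a separate decision for the sponsor.

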### Pre-Intervention Procedures

The study staff member will arrive at bedside, explain the risks and benefits of the study, and will obtain informed consent. Next, a physician or authorized study staff member will collect blood pressure and pulse data using standard sphygmomanometers in hospital wards, and will ask the patient to report current pain level on a 0 to 10 scale. We will also assess coping (Roberts, 2010) by asking "How are you coping with your labor?" We will also obtain all pain ratings collected and documented in the EHR during the current hospitalization up to 96 hours

before the intervention. Additionally, the study staff member will administer the **Quantitative Patient Survey** -- included at the end of this document and based on the NIH PROMIS Global Health Survey (10 items) and Childbirth Self-Efficacy inventory (15 items).

When a patient expresses interest in the study, she will then undergo randomization to either the VR arm or the Control arm of the study. Group assignments will be maintained inside sequentially numbered, sealed, opaque envelopes. After informed consent, study personnel will then open the assigned envelope and the study treatment will be revealed. Patients, providers, and study personnel will not be blinded to the assigned intervention.

For those patients randomized to VR, the study staff member will explain the use of the Samsung VR goggle set, and thereafter will allow the patient to use the device freely for up to 30 minutes. Intervals of 2-5 minutes is suggested for first-time use, and patients will be to allowed to discontinue it at any time as long as they are not experiencing any discomfort or side effects (dizziness, motion sickness, etc.). The study staff member will be present at all times, and will work with hospital staff as necessary to ensure the patient is receiving appropriate clinical care throughout the duration of the intervention.

For those patients randomized to the Control, the study staff member will explain that their assignment has been to the standard of care for which is no specific dedicated intervention at this time. Rather their intervention will only be further assessment of their pain scores, vitals, and medication use.

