#### Post-Intervention Procedures

At the completion of either the VR or the Control intervention, the patients will be asked to Quantitative Patient Survey again, this time asking whether the preceding intervention would affect their responses to the questions.

A physician or authorized study staff member will collect blood pressure and pulse rate using standard sphygmomanometers in hospital wards, self-reported pain vitals, and assess coping. Then, the study staff member will ask the patient a series of questions about their experience (See Post-Intervention surveys in Additional Information).

Patients will spend 40 minutes to 1 hour with a member of the study staff during the inpatient stay, including both the initial intervention and interview time. Responses to the qualitative interview will not be audio- or video-recorded; instead, responses will be transcribed and later coded using qualitative data analysis software by study staff. Vitals collected immediately before and after the intervention will be recorded electronically; pain ratings up to 96 hours before and after intervention will be retrieved from the EHR by authorized study staff for analysis. All survey responses will be entered into a secure Redcap on a protected CSHS server.

Between participants, the VR device will be cleaned as detailed below.

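### Secondary outcome 5 includes vital signs during the session, but the analysis text names no variable or test for them, and the after-session comparison is not adjusted for baseline

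*Combined protocol and SAP*

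**What the plan says.** All places are in the combined protocol and SAP.

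- **Outcomes and Data Collection, secondary outcome 5:** "Vital sign changes during and after the intervention including heart rate and blood pressure".
- **Same section, data item 4:** vital signs are collected "before, during (continuous pulse oximeter and blood pressure measurements every 10 minutes) and after the intervention".
- **Pre-Intervention Procedures:** staff "will collect blood pressure and pulse data using standard sphygmomanometers in hospital wards". For controls, "Rather their intervention will only be further assessment of their pain scores, vitals, and medication use"; no times are given.
- **Post-Intervention Procedures:** "A physician or authorized study staff member will collect blood pressure and pulse rate using standard sphygmomanometers in hospital wards", and "Vitals collected immediately before and after the intervention will be recorded electronically". In-session readings are not mentioned.
- **Sample Size Calculations (which holds the analysis text):** for pain, blood pressure and pulse, "We will compute change scores for each of these measures and also compare these patients to the Control group". If data are normal, "we will use a paired Student's t test for comparisons pre- and post-intervention", with two-sample t tests between arms. The signed-rank and rank-sum tests are the fallback for skewed data.
- **Session length:** Pre-Intervention Procedures allows up to 30 minutes. VR Software gives a 20-minute limit on use per session. Both suggest 2 to 5 minutes for first use.
- **Subject Participation End:** participation closes when the woman chooses to stop, or at 30 minutes.

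**The concern.** The outcome has two parts, during and after, and the data collection list supports both. The analysis text carries only the after part in recognisable form. Nothing says whether the in-session readings are to be summarised as a mean, a peak, a last value or a repeated-measures profile, what they are compared with, or at what times controls are read. If they are analysed anyway, that choice will be made with the data in view.

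The Background section gives distraction as the mechanism, so readings taken while the headset is on are closest to the effect of interest. The after reading is also loosely timed. Participation can end early, so a woman in the VR arm who stops after a few minutes may have her after reading sooner after the start than a control observed for the full period.

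A second, smaller matter is that the between-arm comparison uses a raw change score. With 20 women per arm, precision that costs nothing is worth having.

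**Working it through.** **Consistency check**

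| Step | During | After |
|---|---|---|
| Secondary outcome 5 | named | named |
| Data item 4 | pulse oximetry, blood pressure every 10 minutes | named |
| Pre- and Post-Intervention Procedures | no instruction | taken and recorded |
| Within-arm test | none named | paired pre/post |
| Between-arm test | change score, time points undefined | change score, time points undefined |

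**How many in-session blood pressures a woman can give**

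Assume readings at 10, 20 and 30 minutes from session start. The count is the whole part of (session minutes / 10).

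- 2 to 5 minutes (suggested first use): 0
- 20 minutes (VR Software limit): 2
- 30 minutes (Pre-Intervention Procedures limit): 3

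**Precision**

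The plan states no SD, target effect or power for vital signs, and its 20 per arm is derived for pain alone, so there is no figure of its own to reproduce. The following rests on assumptions: every reading has variance 1, and any two readings on the same woman have correlation r, with r from 0.5 to 0.7. The small cost of estimating one regression slope is ignored.

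Variance per woman:

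- Change score, post minus pre: 2(1 − r)
- Post reading adjusted for baseline: 1 − r²
- Mean of two in-session readings, adjusted: (1 + r)/2 − r²
- Mean of three in-session readings, adjusted: (1 + 2r)/3 − r²

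| Quantity | r = 0.5 | r = 0.7 | Below change score |
|---|---|---|---|
| Change score | 1.00 | 0.60 | – |
| Adjusted post reading | 0.75 | 0.51 | 25% / 15% |
| Adjusted mean of two | 0.75 − 0.25 = 0.50 | 0.85 − 0.49 = 0.36 | 50% / 40% |
| Adjusted mean of three | 0.67 − 0.25 = 0.42 | 0.80 − 0.49 = 0.31 | 58% / 48% |

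The variance of the difference between arms is 2/20 times each entry, so the percentages carry over unchanged.

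**Splitting the gain**

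Part of the reduction for in-session means comes from baseline adjustment, not from extra readings. Measured against the adjusted post reading, two readings give 1 − 0.50/0.75 = 33% (r = 0.5) or 1 − 0.36/0.51 = 29% (r = 0.7). Three give 1 − 0.42/0.75 = 44% or 1 − 0.31/0.51 = 39%.

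**The case against.** The strongest reply is that the plan is loosely written here and does not discard data. Several stronger readings are tempting, and the documents do not support them.

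- **That only the before and after values are recorded.** Data item 4 lists in-session readings as study data. The sentence in Post-Intervention Procedures names the before and after vitals without excluding others.
- **That the in-session readings are deliberately left out.** The change scores have no stated time points, so a during-minus-baseline score would fit the between-arm text. The defect is an undefined variable.
- **That the change score is the least precise choice.** An unadjusted post reading has variance 1.00, against 0.60 for the change score at r = 0.7 and 1.00 at r = 0.5. At r = 0.7 the unadjusted mean of three in-session readings, (1 + 1.4)/3 = 0.80, is also worse than the change score.
- **That the variance ratios, 1.00/0.42 = 2.4 and 0.60/0.31 = 1.9, are a gain in effective sample size.** That would need the effects during and after the session to be equal, which nothing in the plan says. It would also need three readings, where the 20-minute limit allows two.
- **That a null vital-sign result would tell us almost nothing.** With no SD or target effect stated, this cannot be shown. The outcome names the after period, so the post reading is on target for that part.

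There is also a fair objection to fixed reading times. Participation ends when a woman stops, so later readings in early stoppers are not currently scheduled, and they would be taken with the headset off. This stands. Fixed times change the question from the effect of being in the headset to the effect of being assigned to it. Restricting to in-headset readings would instead leave women with short sessions without a blood pressure and make the VR arm a group selected by duration of use.

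Finally, this is the last of five secondary outcomes, it carries no power claim, and vital signs appear in neither hypothesis statement. That limits the weight of the point.

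**Conclusion.** The point holds in a limited form. A named part of secondary outcome 5 has scheduled data but no in-session procedure, no summary variable and no test. Followed as written, the plan answers only the after part, and does so with an unadjusted change score. This conclusion rests on the text alone.

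The size of the precision gain rests on assumed equal variances and a common correlation of 0.5 to 0.7, and unequal correlations would alter it. Under those assumptions, about 15 to 25% is available from baseline adjustment of readings already taken. The larger reductions of 40 to 58% combine that adjustment with averaging two or three in-session readings. They describe precision and say nothing about whether the during and after effects are of the same size. The matter is minor, and the primary pain outcome is not affected.

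**What to change.** 1. **Post-Intervention Procedures:** state that the in-session readings in data item 4 are recorded in both arms, at the same times from session start. Define session start for controls.
2. **Analysis text under Sample Size Calculations:** for systolic pressure, diastolic pressure and pulse, compare arms on the mean of the scheduled in-session readings, and separately on the post-session reading, each by regression on arm and the baseline value.
3. **Session limits and Subject Participation End:** reconcile the 30-minute limit in Pre-Intervention Procedures with the 20-minute limit in VR Software, since this fixes how many readings exist. Amend Subject Participation End so that scheduled readings continue in women who stop early, and say that the result is the effect of assignment, not of being in the headset.

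The cost is a few extra readings in women who stop early, storage of readings already planned, and a few lines of analysis text. The effect of assignment may be smaller than the effect while wearing the headset, and the report should say so.

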**Virtual Reality in Labor and Delivery for Reduction in Pain**

**NCT03437031**

**Unique Protocol ID: Pro00050082**

**June 25, 2021**

## **Title: Virtual Reality for pain reduction in Labor and Delivery**

**Principal Investigators: [name], [name], [name], [name], MPH and [name], MPH**

### Purpose and Hypothesis

The purpose of this study is to identify whether use of virtual reality devices can improve the pain management of women in labor and delivery. We hypothesize that use of virtual reality devices will result in a reduction in pain medication use, in epidural use, and prolong the duration of time prior to the patient receiving an epidural.

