### Birth Preferences for Pain

What are your plans for coping with labor pain? (circle all that apply)

Acupuncture, acupressure, aromatherapy, biofeedback, hypnosis, massage therapy, hydrotherapy (tub), oral pain medications, IV pain medications, epidural, other

Did you attend childbirth education classes? (Yes/No)

Have you taken classes/training in any of the following methods of coping with labor pain?

Acupuncture, acupressure, aromatherapy, biofeedback, hypnosis, massage therapy, hydrotherapy (tub)

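### The hypothesis covers pain medication by any route, but the only defined medication outcomes count IV medication, so a change of route could pass for a reduction

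*Combined protocol and SAP*

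**What the plan says.** Purpose and Hypothesis predicts that VR "will result in a reduction in pain medication use", with no route named and epidural use listed separately. The Background restates the question as "whether it had any effect on their need for pain medications or choice to receive an epidural", again without a route.

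In Outcomes and Data Collection, the only medication outcomes are secondary outcome 3, "Need for IV pain medication during the intervention", and 3a, "Time to IV pain medication after the intervention". Epidural has its own outcomes, 4 and 4a. Data item 6 is "Pain interventions including time to first use of IV pain medication and first use of epidural".

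Other sections bear on how much non-IV use there could be and whether it would be seen:

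- Birth Preferences for Pain, part of the baseline survey, offers "oral pain medications, IV pain medications, epidural, other" among the coping plans a woman may circle.
- How the research differs from Standard of Care leaves all other pain management open to the patient.
- Exclusion 2 in Study Population and Period is "Use of medications for pain relief prior to the intervention", with no route named.
- Pre-Intervention Procedures says that control patients will be assessed for medication use, with no route named.
- Data Security and Privacy restricts staff to variables that the protocol has already named.

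**The concern.** The question is asked about all pain medication and answered with a count of one route. Before the session, any pain medication disqualifies a woman. Afterwards, only IV medication has a defined outcome.

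What is at stake is the medication claim, the first effect named in Purpose and Hypothesis. If women in one arm take an oral or other non-IV analgesic where women in the other take an IV one, outcomes 3 and 3a will differ between arms although the same number of women were medicated. The reverse pattern would mask a true reduction. Neither could be recognised unless non-IV use is recorded, and no variable for it is named. The open wording of data item 6 also lets abstractors differ in what they collect, in a trial where study staff know the assignment.

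**Working it through.** The plan gives no rate, effect size or power for any medication outcome, so there is no figure to reproduce. The check is a comparison of definitions, followed by arithmetic on what one woman is worth.

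**1. Trace each type of patient through the definitions.**

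| Analgesia after enrolment (no epidural) | Pain medication, as hypothesised | Outcomes 3 and 3a |
|---|---|---|
| None | No | No event |
| IV only | Yes | Event |
| Oral or other non-IV only | Yes | No event |
| Non-IV first, IV later | Yes, from the first dose | Event, but at the later IV time |

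The definitions disagree in the last two rows. The baseline survey foresees oral medication, and nothing in the protocol prevents its use.

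**2. Weight of one woman.** With 20 per arm (Study Population and Period), 1/20 = 5 percentage points.

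**3. A shift of route in one arm (assumed numbers).** Suppose 60% of each arm takes some analgesic: 0.60 × 20 = 12 women, a true difference of zero. If 3 of the 12 in the VR arm use only a non-IV drug and none do in the control arm, the IV-only rates are 9/20 = 45% and 12/20 = 60%. The apparent reduction is 15 points, with no reduction in medication. If the 3 women are in the control arm, the error is 15 points the other way.

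**4. The same non-IV share in both arms (assumed numbers).** Suppose true any-analgesic use is 60% in control and 30% in VR, and a share q of users in both arms takes only non-IV drugs. The IV-only rates are then 0.60(1 − q) and 0.30(1 − q). The plan names no test for these outcomes, so take the usual two-sided 5% normal approximation with n = 20 per arm, where D is the difference in rates and p̄ their mean:

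power = Φ{[D − 1.96√(2p̄(1 − p̄)/n)] / √([p₁(1 − p₁) + p₂(1 − p₂)]/n)}

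For q = 0: D = 0.30, p̄ = 0.45, and (0.30 − 1.96 × 0.1573)/0.15 = −0.055, so power is about 48%.

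| q | IV-only rates | Power |
|---|---|---|
| 0 | 60% vs 30% | 48% |
| 10% | 54% vs 27% | 41% |
| 25% | 45% vs 22.5% | 32% |
| 50% | 30% vs 15% | 20% |

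Even without a differential shift, counting one route weakens the comparison. None of these rates comes from the documents; they show direction and scale only.

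**The case against.** The strongest reply is that the plan does not close the door on other routes. Data item 6 is introduced with an open word, the control-arm text speaks of medication use generally, and epidural is recorded too. A reader might infer that only IV medication will be recorded, and that the limit in Data Security and Privacy bars the rest. The documents do not support this: pain interventions and medication use are both already mentioned, so that limit does not clearly exclude non-IV drugs. This part of the objection stands.

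A reader might also infer that a woman on oral analgesia will be counted as having used no medication. No section says so. Outcome 3 is labelled as IV, and on that label she is correctly classed as having had none. The error arises only when the IV result is used to answer the hypothesis about pain medication, but no other outcome is defined to answer it.

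Three further points have force. The survey item records plans, not use. The frequency of non-IV analgesia is unknown, and an assumed rate for the whole labor could not be carried over to outcome 3, which covers a session of at most 30 minutes. It is tempting to add that the primary pain score would be contaminated by unseen oral doses, but staff attend throughout VR use and medication use is to be assessed, so the documents do not show that such a dose would be missed.

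What the objection does not remove is the mismatch itself. Even if every oral dose is captured, outcomes 3 and 3a as defined leave it out.

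**Conclusion.** The point holds as a mismatch between hypothesis and outcome definition. The hypothesis covers any pain medication, the defined outcomes cover the IV route, and no non-IV variable is named, although one might be captured under the open wording. Followed as written, the plan cannot fully answer its own medication question.

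Each woman who uses only non-IV, non-epidural analgesia shifts her arm's rate by 5 points, and a between-arm imbalance of 3 such women by 15 points. Whether that happens depends on a frequency that the documents do not give. If non-IV use is rare, the numerical effect is small, but the claim would still be wider than the measure. These are secondary outcomes; the conclusion does not extend to the primary pain score.

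**What to change.** In Outcomes and Data Collection:

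- Define secondary outcomes 3 and 3a as any analgesic medication other than epidural, and report IV-only as a subset so that nothing in the present outcome is lost.
- In data item 6, list drug, route and time of first dose, taken from the medication record, in the same way for both arms.
- State in advance which drugs count as analgesics.

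If this is not adopted, limit the medication hypothesis in Purpose and Hypothesis, the matching sentence in the Background and the eventual conclusion to IV medication.

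The cost is a wider filter on the EHR abstraction already planned, plus the work of agreeing the drug list. It adds no visit and no burden for patients. It does change the definition of a secondary outcome, so it should be settled before outcome data are examined.
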